17. DATA ANALYSIS PLAN

Statistical Methods

Primary Statistical Hypothesis

To test the hypothesis that a multidisciplinary team intervention using pre-specified medication

dosing regimens guided by Cardiac Compass-Optivol data will increase the rate of change in beta-blocker and/or diuretic prescription (defined as initiation, termination, or dose adjustment) in the intervention group compared to usual care at 6 months.

Statistical Test Method and Sample Size Considerations

The primary outcome of this study is the rate of change in medical optimization (changes in heart failure medications and dosing) guided by CIED physiologic and patient engagement app data that are used together with pre-specified medication dosing regimens over 6 months. The rate of change in HF medications (beta-blocker, diuretic, and Sacubitril/Valsartan) will be compared between the multidisciplinary team intervention guided by CIED physiologic digital data group and usual care control group using chi-square analysis. We estimate that the rate of medication change will be 10% in the conventional group based on our URMC ICD database, as compared to 60% in the intervention group. Accordingly, a sample of approximately 30 patients will be required to provide a power of 80% and a 2-sided alpha of 0.05, accounting for 10% drop out rate. The comparison of the rate of recurrent medication adjustments between the two study groups will be assessed using negative binomial regression analysis and is expected to result in greater than 80% power (possibly 99%) based on the expected rate of multiple medical changes (at the monthly virtual visits) in the intervention group.

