4.1. SUBJECT POPULATION

Approximately 30 subjects total will be enrolled in this study following a 2:1 ratio (intervention: control). The study will be conducted at the University of Rochester Medical Center. Over 250 patients are newly implanted with a defibrillator per year and over 1,000 patients are followed within the system.

- Gender and Age of Subjects: Male and female subjects aged 18 years to 85 years. We expect to enroll about 25% women.
- Racial and Ethnic Origin: There are no restrictions on race or ethnicity in this study. We expect to enroll about 25% minority subjects.

Inclusion Criteria

- 18 to 85 years of age on the date of randomization
- ICD implantation for primary prevention in patients with ischemic and non-ischemic cardiomyopathy ≥ 3 calendar months from date of enrollment
- SMART Phone or tablet with Bluetooth capability with internet access
- No other identifiable reversible cause explaining the left ventricular dysfunction

Exclusion Criteria

- CRT implanted.
- LVEF $> 45\%$ in the last echocardiogram or other clinic imaging performed.
- Medtronic device generator and/or device components not implanted
- Unstable clinical condition, life threatening arrhythmia
- Heart failure hospitalization within the preceding 3 calendar months
- Cognitive impairment
- Severe renal dysfunction (eGFR < 30 ml/min/m²)

- Serious known concomitant disease with a life expectancy of < 12 calendar months
- Non-ambulatory NYHA class IV
- Pregnancy

Inclusion of Vulnerable Populations:

- Vulnerable populations: Women of childbearing potential are included if they are currently on the medications to be optimized (beta-blockers, diuretics and Sacubitril/Valsartan).

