16. DATA AND SAFETY MONITORING PLAN

An adverse event is any unexpected symptom, sign, illness, or experience that develops or worsens during the course of the study and is possibly or definitely related to study procedures.

Adverse Event Reporting

Investigators shall report to their local IRB, and report in the electronic data collection system within five business days of PI awareness only real or suspected, serious and unanticipated adverse events that are related to participation in the study (i.e. anaphylaxis to medication) Events related to standard of care such as medications side effects do not need to be reported unless severe as defined below. Death of a subject must be reported as an adverse event, per the serious adverse event definition below. The PI is aware that investigators are responsible for reporting to and following the guidance of any other applicable oversight bodies, including the Institutional Review Board (IRB).

Serious Adverse Event Definition

This population is at baseline increased risk of heart failure, death, and poor clinical outcomes. A serious adverse event is defined as any adverse medical experience that results in any of the following outcomes:

- death;
- is life-threatening;
- requires inpatient hospitalization or prolongation of existing hospitalization;
- results in permanent impairment of a body structure or a body function;
- requires medical or surgical intervention to prevent permanent impairment or damage;
- leads to fetal distress, fetal death or a congenital abnormality or birth defect.

Data Safety Monitoring Board

A data and safety monitoring board (DSMB) will be appointed to independently monitor the conduct and the outcome of the trial. The DSMB will be responsible for monitoring the safety and well-being of the patients participating in this study and ensuring the ethical conduct of the trial. Since this study is a pilot project enrolling approximately 30 patients using data already routinely used by clinicians and since the safety endpoints focus on optimizing current standard of care medications, the main focus of DSMB activity will be to monitor for potential increase in unexpected complications during the trial. For patients in the conventional treatment arm, data on clinical events including adverse events, cardiovascular hospitalizations, and death will also be collected and provided to the DSMB for evaluation of risks associated with drug therapy.

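### Does the primary test need to be specified more closely than chi-square analysis for a trial of about 30 patients?

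*Combined protocol and SAP*

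**What the plan says.** The primary analysis is set out under Statistical Test Method and Sample Size Considerations in section 17. The proportions of patients with a change in heart failure medication are to be compared between the intervention group and the "usual care control group using chi-square analysis". That is the whole description of the primary test. Negative binomial regression is named too, but only for recurrent adjustments.

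The same paragraph gives the planning values. For the control arm: "We estimate that the rate of medication change will be 10% in the conventional group based on our URMC ICD database". For the other arm: "as compared to 60% in the intervention group". From these it concludes that "a sample of approximately 30 patients will be required" in order "to provide a power of 80% and a 2-sided alpha of 0.05", with an allowance of 10% for dropout.

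The allocation is given elsewhere, for example in section 4.1: "Approximately 30 subjects total will be enrolled in this study following a 2:1 ratio (intervention: control". Section 16 describes the scale of the study: "Since this study is a pilot project enrolling approximately 30 patients".

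**The concern.** Chi-square analysis can mean the uncorrected Pearson test or the version with Yates's continuity correction. Many statisticians would also move to Fisher's exact test once expected counts are small. In a large trial these agree. Here the control arm has about nine evaluable patients, and at that size they can give different verdicts.

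Software defaults add to the worry. For 10 of 18 against 1 of 9, one intervention patient short of the table nearest the plan, scipy's chi2_contingency at its default returns p = 0.072 because it applies the correction. The statsmodels routine proportions_chisquare returns p = 0.027 because it does not. Two analysts could both claim to follow section 17 and report opposite primary results. If the version were picked after the data had been seen, the stated two-sided 5% level would lose some of its meaning.

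**Working it through.** **Inputs.** From section 17: control rate 10%, intervention rate 60%, about 30 patients, 80% power, two-sided alpha 0.05, 10% dropout. From section 4.1: 2:1 allocation. Evaluable patients: 30 × 0.9 = 27, split 18:9. The plan does not print this split; it assumes equal dropout in both arms. The outcome is taken as one yes/no per patient, which the two percentages and the choice of test imply.

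**The plan's figure by formula.** With control size n and intervention size 2n, the pooled rate is (0.1 + 2 × 0.6)/3 = 0.433. The pooled standard deviation term is √(0.433 × 0.567 × 1.5) = 0.607, and the unpooled term is √(0.09 + 0.24/2) = 0.458. Then

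n = (1.96 × 0.607 + 0.842 × 0.458)² / 0.5² = 9.9, rounded up to 10.

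That is 10 + 20 = 30 before dropout, or 30/0.9 = 33.3, so 34, after it. The normal approximation gives 80.4% power at 20:10 and 75.1% at 18:9. The continuity-corrected formula needs 39 before dropout and 44 after it.

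**Exact power.** All 19 × 10 = 190 outcomes at 18:9 (and all outcomes at 20:10) were enumerated with binomial probabilities at 60% and 10%. An outcome counts as significant if p ≤ 0.05.

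| Test | Power at 18:9 | Power at 20:10 | Maximum type I error at 18:9 |
|---|---|---|---|
| Pearson, uncorrected | 78.9% | 81.5% | 6.3% |
| Chi-square with Yates correction | 59.1% | 67.7% | 1.9% |
| Fisher exact | 71.9% | 73.6% | 3.9% |
| Boschloo | 74.0% | not computed | 4.8% |

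Only the uncorrected Pearson test is close to 80%. Its type I error at 18:9 is 4.1% when both arms have the plan's control rate of 10%, and 5.6% when both have 20%. The 6.3% maximum occurs at a common rate of 27% or 73%. At 20:10 the maximum is 5.2%.

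**Small expected counts.** At the planned rates the expected number of control patients with a change is 9 × (10.8 + 0.9)/27 = 3.9. Over all tables at 18:9, the smaller expected control count is at most 9 × 13/27 = 4.33, so the usual threshold of 5 is never reached.

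**How often the verdicts differ.** Every disagreement runs the same way: Pearson is significant and the other test is not.

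| Split and rates | Pearson v. Yates | Pearson v. Fisher |
|---|---|---|
| 18:9, 60% v. 10% | 19.8% | 7.0% |
| 20:10, 60% v. 10% | 13.7% | 7.9% |
| 18:9, 50% v. 10% | 28.8% | 14.6% |
| 18:9, 70% v. 10% | 9.5% | 1.8% |

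**Single tables at 18:9.** For 10/18 v. 1/9 the cross-product difference is 10 × 8 − 1 × 8 = 72.

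- Uncorrected: χ² = 27 × 72² / (18 × 9 × 11 × 16) = 4.91, p = 0.027.
- Corrected: the difference becomes 72 − 13.5 = 58.5, so χ² = 3.24, p = 0.072.
- Fisher: p = 0.042.

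Pearson and Fisher therefore agree on this table. For 11/18 v. 1/9, the table nearest the plan, all three tests are significant (0.014 Pearson, 0.040 Yates, 0.019 Fisher). Pearson and Fisher part at 9/18 v. 1/9 (0.049 and 0.091).

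**The case for a change.** The strongest case for a change is that section 17 claims a formal test with stated power and alpha, so the test ought to be identified. Naming it would take one clause. The ambiguity is not confined to one convenient split: the Pearson–Yates disagreement lies between about 11% and 24% across the splits examined (11.2% at 18:10, 24.2% at 16:8). It also grows if the effect is smaller than planned. Supplying Fisher because counts are small would lower the power from about 79% to about 72%.

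The arithmetic stands, and so does the observation that the wording is incomplete. The claim that the test is open is weaker. Unqualified chi-square ordinarily means Pearson's statistic, and the stated power points the same way. The large percentages come from the Yates version, which falls about 20 points short of the stated power at 18:9 and is very conservative there. The more usual small-sample alternative is Fisher, and at the planned rates the verdict then changes in only 7% to 8% of trials.

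A second objection is that Pearson can exceed 5% at 18:9. It can, by up to 1.3 points at the worst common rate, but not at the plan's own control rate. Replacing it with Fisher or Boschloo would keep the error at or below 5% at a cost of 7 or 5 points of power. Statisticians disagree over that trade-off, and choosing Pearson is not an error.

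**Conclusion.** No change to the plan is called for. Section 17 leaves out a detail, but its own figures supply it: the uncorrected Pearson test gives exact power of 78.9% at 18:9 and 81.5% at 20:10, in line with the stated 80%, and the corrected version does not. An analyst following the plan would use the uncorrected test, and the power statement would be right for it. Writing the version down would not alter the design, the sample size or the expected result.

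What remains is modest. At the planned rates, substituting Fisher would reverse a significant Pearson result in about 7% to 8% of trials, and substituting the continuity-corrected test would do so in about 14% to 20%. At the result nearest the plan all three tests agree. The study is a pilot, which limits what rests on a p-value close to 0.05.

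These figures assume a yes/no outcome per patient, 30 enrolled at 2:1, equal dropout of 10% (18:9) or none (20:10), and true rates of 60% and 10%. With a smaller true effect the choice of version would matter more (14.6% against Fisher at 50% v. 10%). The natural reading of the plan would still be the uncorrected test.

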Patients are randomized 2:1 into:

An Intervention Group

The clinical management of the intervention group will be comprised of the following:

- A study care-team, comprised of a Cardiologist, an Electrophysiologist, a Registered Nurse, and study coordinator who will receive monthly physiologic and functional reports derived from Medtronic CIEDs incorporating Cardiac Compass and OptiVol monitoring.

- The study team will also be provided with patient-specific data derived from patient reported outcomes that include symptoms, quality of life scores, and PROMIS data if available. PROMIS®, a tool developed for use by the National Institutes of Health provides quality of life data, and is part of standard clinical care at the University of Rochester Medical Center Cardiology Department for patients. This is a survey patients have the option of filling out at clinic visits and available through the electronic medical record.
- The Datos app platform will be used to conduct a separate Quality of Life study survey and weekly e-survey REDCap may also be used as an additional resource..
- A pre-specified management regimen based on standard clinical practice will be provided to the study team in which medical management including medication dosing (focusing on beta-blockers and diuretics) will be monitored and modified using CIED and OptiVol data (see Figure 1 and footnote* at end of document). This is based on current and accepted clinical practice.
- The study team will contact the patients on a monthly basis for 4 monthly virtual visits. Based on CIED and patient engagement data, the study team will adjust medications and dosages, and optimize activity/ exercise steps. All medication changes resulting from the virtual visits will be updated in the subject's electronic medical record and communicated by medical chart messaging or URMC email based on the patient physician's preference.
- All study team contacts with the patients will be virtual, using telecommunication or E-communication. These options include URMC approved Zoom portal (currently used for URMC telemedicine clinical care), phone, or email. If the telemedicine call (preferred method) is disconnected, phone or email will be utilized. These e-communications will occur using an existing HIPAA compliant platform to improve efficiency, patient engagement, and reduce study costs while preserving data quality.

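### At the planned 2:1 allocation, 30 patients is the number needed with no drop-out, so the stated 80% power is not met once the plan's own 10% loss is applied

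*Combined protocol and SAP*

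**What the plan says.** The sample-size paragraph of section 17 (Data Analysis Plan) compares the proportion of patients with a heart failure medication change between the intervention group and the "usual care control group using chi-square analysis". The assumed rates are given as "We estimate that the rate of medication change will be 10% in the conventional group" and "as compared to 60% in the intervention group". From these it concludes that "approximately 30 patients will be required to provide a power of 80% and a 2-sided alpha of 0.05, accounting for 10% drop out rate". The paragraph gives no formula, no allocation ratio and no continuity correction.

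The allocation ratio is stated elsewhere. Section 4 (Study Design) says "Patients are randomized 2:1 into" the two groups, and section 4.1 (Subject Population) says "Approximately 30 subjects total will be enrolled in this study following a 2:1 ratio (intervention: control"). The 30 is therefore an enrolment figure, 20 intervention and 10 control.

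**The concern.** Unequal allocation costs power, so a total that suffices at 1:1 may not suffice at 2:1. The sample-size paragraph does not mention the ratio, and 30 is close to what an equal-allocation calculation gives with drop-out included. If the ratio was left out, the 30 has no room for the 10% loss it claims to cover.

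The primary comparison is a formal two-sided test, and this is the only power attached to it. With 9 or 10 controls a non-significant result is quite possible even if the assumed rates are true, and readers would judge it against 80% power that the enrolled sample does not provide on the plan's own assumptions.

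**Working it through.** **Inputs.** From section 17: control rate p_C = 0.10, intervention rate p_I = 0.60, two-sided alpha 0.05 (z = 1.96), power 80% (z = 0.8416), drop-out 10%, chi-square test. From sections 4 and 4.1: intervention to control ratio r = 2, about 30 enrolled.

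**Formula.** For an uncorrected chi-square test, the pooled-variance formula for the number of controls is

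n_C = [1.96·√(p̄(1−p̄)(1+1/r)) + 0.8416·√(p_C(1−p_C) + p_I(1−p_I)/r)]² / (p_I−p_C)², with p̄ = (p_C + r·p_I)/(1+r).

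**Can the plan's 30 be reproduced?**

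- *At the planned 2:1.* p̄ = (0.10 + 1.20)/3 = 0.4333. n_C = [1.96·√(0.4333 × 0.5667 × 1.5) + 0.8416·√(0.09 + 0.24/2)]² / 0.25 = 9.92. The total is 29.8 unrounded, or 10 + 20 = 30, and this is the evaluable number. With drop-out, 29.8/0.9 = 33.1 unrounded; 30/0.9 = 33.3, so 34 in whole patients.
- *At 1:1.* p̄ = 0.35, and the formula gives 13.04 per arm. The total is 26.1 unrounded, and 26.1/0.9 = 29.0. With whole patients per arm it is 28 evaluable and 32 enrolled.

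Like for like, enrolment is 33.1 at 2:1 against 29.0 at 1:1 unrounded, or 34 against 32 in whole patients. The stated 30 lies nearer the 1:1 result. That suggests the ratio was omitted, but the documents do not say so.

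Other methods at 2:1 with drop-out included give 44 with a continuity correction, 27 one-sided, 22 with unpooled variance, and 30.8 by arcsine (34 in whole patients at exactly 2:1). None of these is the two-sided chi-square calculation that the plan names.

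**Power after the plan's own loss.** Ten per cent off 20 + 10 leaves 18 + 9 = 27. Rearranging the formula, power = Φ[((p_I−p_C)·√n_C − 1.96·√(p̄(1−p̄)·1.5)) / √(0.09 + 0.12)].

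- n_C = 10: (0.5 × 3.162 − 1.190)/0.458 = 0.855, so power is 80.4%.
- n_C = 9: (0.5 × 3 − 1.190)/0.458 = 0.677, so power is 75.1%.

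**Exact power**, by enumerating all outcomes under the two binomial distributions:

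| Evaluable (intervention v control) | Formula | Exact, uncorrected chi-square (maximum size) | Exact, Fisher (maximum size) |
|---|---|---|---|
| 20 v 10 | 80.4% | 81.5% (5.2%) | 73.6% (3.3%) |
| 18 v 9 | 75.1% | 78.9% (6.3%) | 71.9% (3.9%) |

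At 18 v 9 the arcsine approximation gives 78.9% and the Yates-corrected chi-square 59.1% (exact). The choice of test matters here: under the pooled rate the expected number of controls with a change is 9 × 0.4333 = 3.9, below 5, where an exact or corrected test is often preferred.

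**The case against.** The strongest reply is that the gap depends on method and is small. Section 17 names a chi-square test but no formula, and the exact power of the uncorrected test at 18 v 9 is 78.9%, about one point under target. Some other splits reach 80% by that calculation: 18 v 10 gives 80.4%, 17 v 10 gives 83.7% and 20 v 9 gives 80.0%. This is a pilot, and the plan says approximately 30 throughout. This stands as a limit on the size of the problem. It does not rescue the statement. The natural split after 10% loss is 18 v 9, which falls below 80% under every method tabulated. The splits that pass need loss confined to one arm or fewer than three patients lost. The maximum size of the uncorrected test at those splits is 5.3%, 6.3% and 5.2%, so all exceed the stated 0.05.

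A second reply is that 10% loss of primary-outcome data may not happen. Sections 4 and 7 collect medication data from the electronic record through 12 months, and section 13 allows withdrawal as lost to follow-up only when data are missing for 7 months, longer than the 6-month outcome window. This has force. But section 13 uses data only up to the date of withdrawal and does not say that chart collection continues afterwards. If nobody is expected to be lost, the drop-out allowance should not be in the sentence. On either reading the sentence needs changing.

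The 1:1 origin of the 30 is a guess, and the conclusion does not rest on it.

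**Conclusion.** The concern holds. At 10% v 60%, two-sided 0.05 and 2:1 allocation, 30 is the evaluable requirement for 80% power. Including 10% drop-out, the requirement is 33 to 34 enrolled. Enrolling 30 and losing 10% leaves 18 v 9 and about 75% power by the standard formula, with a range of 72% (Fisher, exact) to 79% (uncorrected chi-square, exact). The shortfall is about 4 patients, or about 5 power points by the formula: modest, but in the only power claim made for the primary comparison.

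This rests on the plan's own rates, on loss falling in proportion across the arms, and on lost patients contributing nothing to the primary analysis. If all 30 are analysed, power is about 80% by the formula and by the exact uncorrected test, and 73.6% by Fisher.

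**What to change.** Rewrite the sample-size sentence in section 17 so that it names the formula or test version, the 2:1 ratio and the evaluable numbers. One of two versions will do:

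- *If drop-out is to be allowed for:* about 30 enrolled at 2:1, leaving 27 evaluable (18 v 9) after 10% loss, gives about 75% power by the pooled two-proportion formula; exact power is 72% with Fisher's test and 79% with the uncorrected chi-square test.
- *If every randomised patient will be analysed from the medical record:* remove the drop-out allowance, say that chart data cover all randomised patients for the 6-month outcome, and state 20 v 10 with about 80% power.

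The cost is one sentence and, under the first version, a slightly less favourable power figure. No extra patients, procedures or analyses are needed. Keeping 80% power after 10% loss by the same formula would instead mean enrolling about 34, but a pilot need not do that if it reports its power correctly.
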